#### 8.2.3 Expectedness

#### 8.2.3.1 Adverse Drug Reactions Commonly Seen from Naltrexone (MIMS)

- Difficulty sleeping
- Anxiety
- Nervousness
- Abdominal pain/cramps
- Nausea and/or vomiting
- Low energy
- Join and muscle pain
- Headache
- Loss of appetite
- Diarrhea
- Constipation

- Increased thirst
- Increased energy
- Depressive mood
- Irritability
- Dizziness
- Skin rash
- Delayed ejaculation
- Erectile dysfunction
- *Reduced sexual desire*
- Chills

#### 8.2.3.2 Adverse Events Commonly Seen Following Implantation procedure

- Local inflammatory reaction; itchiness, redness, heat or swelling
- Wound site Infections
- Hematoma

#### 8.2.3.3 Adverse Events Rarely Seen Following Implantation procedure

- Allergic reactions to suture material
- Implant removal for infections or allergic responses
- Implant removal for psychological reasons.

#### 8.2.3.4 Adverse Events Commonly Seen from Poly Lactide Polymer

• Local inflammatory reaction; itchiness, redness, heat or swelling

# 8.3 TIME PERIOD AND FREQUENCY FOR EVENT ASSESSMENT AND FOLLOW-UP

The occurrence of an AE or SAE may come to the attention of study personnel during study visits and interviews of a study participant presenting for medical care, or upon review by a study monitor.

All AEs including local and systemic reactions not meeting the criteria for SAEs will be captured on the appropriate CRF. Information to be collected includes event description, time of onset, clinician's assessment of severity, relationship to study product (assessed only by those with the training and authority to make a diagnosis), and time of resolution/stabilization of the event. All AEs occurring while on study must be documented appropriately regardless of relationship. All AEs will be followed to adequate resolution.

Any medical condition that is present at the time that the participant is screened will be considered as baseline and not reported as an AE. However, if the study participant's condition deteriorates at any time during the study, it will be recorded as an AE.

Changes in the severity of an AE will be documented to allow an assessment of the duration of the event at each level of severity to be performed. AEs characterized as intermittent require documentation of onset and duration of each episode.

The PI will record all reportable events with start dates occurring any time after informed consent is obtained until 7 (for non-serious AEs) or 30 days (for SAEs) after the last day of study participation. At each study visit, the investigator will inquire about the occurrence of AE/SAEs since the last visit. Events will be followed for outcome information until resolution or stabilization.

In the event of study discontinuation for any reason, any ongoing AEs will be followed until resolution, or in the event of removal of the OLANI for at least 4 weeks after the removal, until deemed stable by the PI, or until the participant is deemed by the PI to be lost to follow-up. If, in the opinion of the PI, it is necessary to monitor a participant beyond the safety follow-up visit, the follow-up period may be extended as necessary. In such instances, the sponsor and the PI will agree to an acceptable follow-up schedule. The PI must maintain a record of all participants who fail to complete the study. The reason for study discontinuation will be made on the appropriate CRF.

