#### 2.1.6.2.2 Conclusions

The ADR and SAE's data reported that the majority of events were due to inflammatory reactions, with about 11.26% (58 in 515) of treatments recording an inflammatory reaction. Of these, the majority could be classified as mild enough to require no further intervention or to be managed with standard oral treatment (prednisolone). Only 1.94% (10 in 515) of treatments could be classified as being more severe and requiring greater intervention of;

'fluid drainage/site cleaned' 0.97% (5 in 515), 'non-surgical removal' 0.58% (3 in 515) or surgical removal 0.38% (2 in 515).

The majority of inflammatory reports occur within the first 60 days of implantation with peak values around the 56 day mark. It should also be noted that this data represents reports of inflammatory reactions received by AMPRF either through proactive follow up questionnaires or patients reporting issues to the clinic. Natural attrition of follow up will occur over a period of 365 days and thus the reported inflammatory responses may be under reported in the latter period of the follow up.

After inflammatory reactions, the next most common ADR was related to withdrawal state - opiate 6.21% (32 in 515) and other associated drug withdrawal symptoms (Insomnia, Anxiety, Depression and Nausea) 7.96% (41 in 515).

Overall it can be concluded that the OLANI is safe and that the perception of efficacy amongst patients has outweighed any perceived inconvenience arising from the mild inflammatory reactions that have been observed. A method for treatment of inflammatory responses is effective with only a small amount of procedures requiring removal of an implant for an unresolved inflammatory response. It is also important to have good treatment plans in place to help patients post implantation to deal with the expected withdrawal symptoms and adjustment to a change in lifestyle from opiate dependence.

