#### **3.2 SECONDARY OBJECTIVES**

• To characterize the safety profile (i.e. AEs, laboratory results, wound site and inflammatory response rates) of the OLANI.

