#### 5.4.2.1 Participant Monitoring and Removal from Study

Medical staff will assess and communicate with the study PI the appropriateness for continuation in the research study on a continuous basis and will remove from the trial participants with significant clinical deterioration or noncompliance of a type which could be dangerous. Criteria for removal from the study will include:

1. Clinical deterioration which cannot be managed safely in the context of outpatient treatment. This would include a participant who becomes suicidal, or a participant

who goes on severe drug binges (including non-opiate drugs), endangering him/herself.

- 2. Elevation of liver enzymes > 3 times normal. The PI or a study physician is available 24 hours/day by phone and/or beeper in case of emergency.
- 3. Participant becomes pregnant. In case of incidental pregnancy, the participant will remain in the study and will be followed until the resolution of pregnancy. To reduce unnecessary procedures, we will stop PK blood draws, unless clinically indicated, however the safety monitoring will continue. In addition, we will collect safety information related to the pregnancy and birth outcomes. After finding an incidental pregnancy the removal of the implant will be offered to the participant and the participant will decide how best to proceed in consultation with her obstetrician. The decision regarding the pregnancy will affect the decision whether or not to remove the implant at any point during the pregnancy. The risk of anesthesia differs during different times during pregnancy, however the risks of anesthesia and the risks of removal are both minimal.

If a participant becomes pregnant, PK labs will no longer be collected, but the participant will be followed for safety monitoring for the remainder of the study.

For those who withdraw from the study, (data collection and / or treatment) there are two main options:

- **Option 1:** Withdrawing from data collection and no further contact with study personnel. This carries the least amount of risk, with option 2 carrying some risk.

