- **Option 2:** Removal of the study medication via surgical procedure. Whilst removal of the study medication is straightforward in the early stages (up to about 10 days), removal after this becomes more complex as the OLANI biodegrades. Later procedures require a general anesthetic (with access to OR facilities) and may result in a large scar certainly larger than not removing the implant but the extent depends on the amount of tissue to be excised. The risks associated with general anesthetic vary between people, but about 20% of those receiving general anesthesia have minor AEs and 0.2% have major AEs including death. If removal of the implant is the only acceptable option to the participant, this will be arranged through either Columbia University Medical Center or another local hospital.

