#### 7.3.7 Early Termination Visit

Any participants that are withdrawn will be required to attend the SURC clinic for an early termination /withdrawal visit as outlined in Table 7-1. Participants will be advised of their options as outlined in in section 5.4.2.

A follow-up visit may be conducted 30 days after the last scheduled on-study visit and is required only if a participant has ongoing AEs or laboratory abnormalities at the last on-study visit. An in-clinic follow-up visit must be conducted 30 days after the last scheduled on-study visit for an AE requiring laboratory testing for participants with the following conditions at the last on-study visit: ongoing AEs, SAEs regardless of attributability, any laboratory abnormalities considered to be AEs or potentially harmful to the participant. For in-clinic follow-up visits, assessments performed should reflect what is considered medically necessary to assess the event(s).

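### Non-serious implant-site reactions starting more than 7 days after an early exit under withdrawal Option 1 are not systematically captured, so a crude inflammatory response rate would be biased low

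*Combined protocol and SAP*

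**What the plan says.** Section 8.3 has the investigator record events with onset from consent "until 7 (for non-serious AEs) or 30 days (for SAEs) after the last day of study participation". After a discontinuation it follows AEs that are already ongoing. It sets no rule for seeking new ones, although the PI may extend monitoring on a schedule agreed with the sponsor.

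For participants who withdraw, section 5.4.2.1 states that "there are two main options". Option 1 is "Withdrawing from data collection and no further contact with study personnel". Option 2 is "Removal of the study medication via surgical procedure". Since removal is the alternative, Option 1 leaves the implants in place.

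Section 7.3.7 opens with "Any participants that are withdrawn will be required to attend the SURC clinic for an early termination" visit, and Table 7-1 marks AE monitoring and a wound/implant site assessment there. The visit 30 days later "is required only if a participant has ongoing AEs or laboratory abnormalities at the last on-study visit". Section 7.3.10 and note 9 to Table 7-1 set the same condition. Section 7.3.10 also invites anyone else with questions about the implant to a meeting.

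The secondary objective (3.2) includes "wound site and inflammatory response rates". Section 10.4.4 plans a frequency, with no denominator, time at risk or censoring rule. On timing, section 2.1.6.2.2 says: "The majority of inflammatory reports occur within the first 60 days of implantation with peak values around the 56 day mark".

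**The concern.** A 7-day onset window suits a drug whose exposure ends when participation ends. Here exposure continues after exit unless the implants are removed, and section 6.1.9 gives the duration of therapy as 540 days. A participant who leaves at Day 30 with a quiet site and reacts at Day 56 would be counted as having had no reaction.

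The rate at stake is part of the secondary objective, and section 2.1.5 reports that an earlier trial of second-generation implants was suspended because of such reactions. In the sponsor's data they are almost all non-serious, so the 7-day limit governs them, not the 30-day one. Section 2.1.6.2.2 accepts the mechanism for its own historical data: it warns that loss to follow-up may hide later reactions.

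**Working it through.** **Inputs from the protocol**
- Historical reaction rate p (2.1.6.2.2): 58/515 = 11.26%, which reproduces the stated figure.
- Planned size (5.3.1): 20 enrolled for 10 completers; 10/(1 − 0.5) = 20, which also reproduces.
- Expected reactions in 20 participants: 20 × 0.1126 = 2.25.
- Share non-serious: Table 2-4 has 96 events coded as inflammatory reaction due to implants and Table 2-5 has 1, so 96/97 = 99.0%. The two tables do not overlap: their unique totals, 263 + 15 = 278, match Table 2-3.

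**Assumptions (not in the documents)**
- q: share of participants who leave early with implants in place.
- F: share of reactions with onset by exit + 7 days.
- p carries over from the historical patients to this trial.

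**Formula.** Expected observed crude rate over all implanted participants = p × [(1 − q) + q × F]. The relative loss is q × (1 − F).

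| q | F = 0 | F = 0.5 | F = 0.9 |
|---|---|---|---|
| 0.10 | 10.14% | 10.70% | 11.15% |
| 0.25 | 8.45% | 9.85% | 10.98% |
| 0.50 | 5.63% | 8.45% | 10.70% |

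**Tying F to exit day.** Let a share s of onsets fall evenly within 60 days and the rest evenly from Day 60 to Day 365. The text says only that a majority fall within 60 days, so s runs from 0.51 to 0.90. Then F(t) = s × t/60 up to Day 60, and s + (1 − s) × (t − 60)/305 after it, with t = exit day + 7.

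Worked case, exit at Day 30 (t = 37), q = 0.5:
- s = 0.51: F = 0.51 × 37/60 = 0.315; rate = 11.26% × (0.5 + 0.5 × 0.315) = 7.4%.
- s = 0.90: F = 0.90 × 37/60 = 0.555; rate = 11.26% × (0.5 + 0.5 × 0.555) = 8.8%.

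| All exits at (q = 0.5) | Expected observed rate |
|---|---|
| Day 14 | 6.6 to 7.4% |
| Day 30 | 7.4 to 8.8% |
| Day 56 | 8.5 to 10.7% |
| Day 180 | 9.7 to 10.9% |
| Spread evenly over 540 days | 10.1 to 10.8% |

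In expected events, the loss is 20 × p × q × (1 − F). For Day 30 exits that is 2.25 × 0.5 × (1 − 0.555 to 1 − 0.315) = 0.5 to 0.8. For evenly spread exits, with mean F of 0.792 to 0.924, it is 0.1 to 0.2.

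**Effect of a 30-day window alone.** For Day 30 exits, t = 60 and F = s, so the rate becomes 11.26% × (0.5 + 0.5 × 0.51) = 8.5% to 11.26% × (0.5 + 0.5 × 0.90) = 10.7%. It recovers part of the loss, not all.

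**Provisions set side by side.** Table 7-1 marks AE monitoring at the 30-day AE Follow-up visit. Section 8.3 counts its 7 days from the last day of participation, which is not defined, while 7.3.7 and 7.3.10 count 30 days from the last scheduled on-study visit. Whether a non-serious onset on days 8 to 30 is recordable depends on that definition. Separately, 7.3.7 makes an in-clinic 30-day visit mandatory for some leavers, which Option 1 does not allow for.

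**The case against.** Several safeguards exist. Withdrawn participants have a site assessment and AE check at the early termination visit. Onsets within 7 days, and SAEs within 30, are recordable. The PI may extend monitoring, and a voluntary meeting is offered. The riskiest period is closely watched, with nine outpatient visits from Day 4 to Day 56, each with a site assessment, and attendance payments that rise with each visit. The 11.26% comes from opioid-dependent patients given an average of 2.49 implants, not healthy volunteers given two. The expected loss is under one event in every dated scenario above. All of this stands, and it limits the size. But the extension and the meeting are discretionary, and neither is a systematic search for new reactions.

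Four stronger readings are tempting, and the documents do not support them.
- *Withdrawal always means no contact with implants in place.* That is Option 1 only; Option 2 removes them, and the text calls these the main options.
- *Option 1 contradicts the early termination visit.* Section 7.3.7 has participants advised of their options in connection with that visit, so the end of contact can follow it.
- *Table 7-1 flatly contradicts 8.3.* With the last day of participation undefined, this is an ambiguity: attending the AE Follow-up visit might itself count as participation.
- *The 50% expected non-completion is an early-exit rate.* Completion also requires 75% of samples and two levels below 0.1 ng/mL, so a participant may stay under observation and still not complete.

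The downward bias also depends on the denominator. It follows for a crude rate over all implanted participants; an analysis that censors at exit need not share it. Section 10.4.4 specifies neither.

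**Conclusion.** The gap is real but narrow. It concerns participants who leave early under Option 1 with implants in place and then have a new non-serious site reaction more than 7 days after their last day of participation. For them the plan has no systematic capture, and a crude rate over everyone implanted would be too low.

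The size cannot be fixed from the documents, because they give neither the early-exit share nor the full distribution of onset times. Taking half of participants as early leavers is an upper assumption. Under it, the understatement is appreciable when exits come before about Day 60 and small when they are spread over the study. This is a worthwhile, cheap improvement to safety capture and reporting. It does not undermine the trial.

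**What to change.** - **5.4.2.1:** add an option to stop visits and PK draws but accept remote AE and implant-site contact to the planned Day 540. Let Option 1 apply only when that contact is declined, and reconcile it with the mandatory 30-day visit in 7.3.7.
- **8.3:** define the last day of study participation and reconcile it with the AE monitoring marked at the AE Follow-up visit in Table 7-1. For those leaving with implants in place, record new non-serious AEs for at least 30 days after exit, and implant-site reactions for as long as the remote contact continues.
- **10.4.4:** report the inflammatory response rate with time at risk, censoring at exit, and give the number of exits with implants in place. Censoring assumes that leaving is unrelated to the risk of a reaction, so that count is needed to judge the result.

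The elements already exist in the protocol: safety follow-up without PK draws for pregnancy (5.4.2.1), remote AE and self-reported site assessment for COVID-19 (note 14 to Table 7-1), and AE identification by telephone (8.1.1). The cost is protocol and consent wording plus brief calls by existing staff to a few leavers. Some will decline, and that right stays intact. No treatment rule changes.

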## 8.4 **REPORTING PROCEDURES**

#### 8.4.1 Adverse Event Reporting

The sponsor will inform the investigator of any new information that may impact the conduct of the trial or have an impact on the ethical acceptability of the trial.

Investigator shall report all AE's on a monthly basis to sponsor and Data Safety Monitoring Board (DSMB) for review.

The sponsor will update the Investigator Brochure regularly with any new safety information relating to the drug.

## 8.4.2 Serious Adverse Event Reporting

All SAEs should be reported immediately to the sponsor, NYSPI IRB, FDA, DSMB except for those SAEs that the protocol or other document (e.g. Investigator's Brochure) identifies as

not needing immediate reporting. The immediate reports should be followed promptly by detailed, written reports. The immediate and follow-up reports should identify participants by unique code numbers assigned to the trial participants rather than by the participants' names personal identification numbers, and/or addresses.

## 8.4.2.1 Management of SAE's

SAEs, as defined by the FDA, will be systematically evaluated at each clinic visit. Any SAE, whether or not related to study medication, will be reported to the NYSPI IRB, FDA & DSMB. The initial SAE report will be followed by submission of a completed SAE report to both institutions.

In the event that a participant either withdraws from the study or the investigator decides to discontinue a participant due to SAE, the participant will have appropriate follow-up medical monitoring. Monitoring will continue until the problem requiring hospitalization has resolved or stabilized with no further change expected, is clearly unrelated to study medication, or results in death. Outcome of SAEs will be reported to the NYSPI IRB, FDA & DSMB as soon as this information becomes available. A summary of the SAEs that occurred during the previous year will be included in the annual progress report to the NYSPI IRB, FDA & DSMB.

## 8.4.3 Reporting of Pregnancy

Reporting of pregnancy will be to the treating physician, PI, NYSPI IRB and DSMB. After finding an incidental pregnancy the removal of the implant will be offered to the participant and the participant will decide how best to proceed in consultation with her obstetrician. The decision regarding the pregnancy will affect the decision whether or not to remove the implant at any point during the pregnancy. The risk of anesthesia differs during different times during pregnancy, however the risks of anesthesia and the risks of removal are both minimal.

## 8.5 STUDY HALTING RULES

#### 8.5.1 Study Termination

The Sponsor reserves the right to close the investigational sites or terminate the study at any time. The Investigator may initiate site closure at any time, provided there is reasonable cause and sufficient notice is given in advance of the intended termination. Reasons for the early closure of an investigational site by the Sponsor or Investigator, or termination of a study by the Sponsor, may include but are not limited to:

- failure of the Investigator to comply with the protocol, the Sponsor's procedures, or GCP guidelines
- safety concerns
- inadequate recruitment of participants by the Investigator

Study termination will be reported to, NYSPI IRB, DSMB and FDA.

## 8.5.2 On-Site Audits

Representatives of the Sponsor's quality assurance department may visit the site to carry out an audit of the study in compliance with regulatory guidelines and the Sponsor's standard operating procedures. Audits and clinical trial monitoring will also be carried out by the CRO, Clinilabs during the trial period. These audits will require access to all study records, including source documents, for inspection and comparison with the CRFs. Participant privacy must, however, be respected. Similar auditing procedures may also be conducted by agents of any regulatory body reviewing the results of this study in support of a regulatory submission. The Investigator should immediately notify the Sponsor if they have been contacted by a regulatory agency concerning an upcoming inspection.

#### 8.6 DATA AND SAFETY MONITORING PLAN ADMINISTRATION

#### 8.6.1 Responsibility for data and safety monitoring (DSM)

The study PI, [name], is required to be present for all DSMB meetings to provide reports for all accumulated data from the trial. The PI will also be primarily responsible for the implementation of any recommendations from the DSMB. The PI will be assisted in this duty by [name], study Medical Monitor.

#### 8.6.2 Frequency of DSM

Ongoing data and safety monitoring will be conducted weekly during research team meetings of the PI with the investigative team. Every three months, the PI and the medical monitor will review the number of participants enrolled, the number who completed the protocol, the number who dropped out of the protocol prior to completion (and reason why), any AEs, procedures for assuring participants privacy and confidentiality, and the quality and integrity of the data collected. Corrective action will be taken if needed. IRB study protocols and informed consent documents will be reviewed annually by the IRB. Reports of enrollment and retention and reporting of AEs are required with these renewals.

In addition, all studies involving human participants are periodically and systematically reviewed by the New York State Quality Assurance Staff. These procedures assure protocol compliance by conducting unannounced reviews of participants' research charts, comparing research charts to the IRB protocol. All SAEs will be reported to the FDA (as appropriate) and the DSMB in a timely fashion.

A separate DSMB (See 8.6.3 for details) will meet quarterly and within a week of any SAEs occurring. Ad hoc meetings may also occur if any study related issues arise during the course of the study.

